#### Please save frequently

b) Describe any animal experimentation and findings leading to the formulation of the study, if there is no supporting human data.

n/a

#### 2. Purpose of the study

a) Provide a brief lay summary of the project in <200 words. The lay summary should be readily understandable to the general public.

Comparing the growth of intra-operative tissue cultures of Cutibacterium Acnes after primary shoulder replacement when using a no-prep control group versus antimicrobial wound gel versus betadine applied to the skin layer after the skin incision has been made. Reducing the bacteria present in the deep tissues at the end of the surgery may prevent infections from developing in the future.

Page numbers from a sponsor's protocol/grant may be referenced in 2b and 2c.

b) List your research objectives (specific aims & hypotheses of the study).

\_\_\_\_\_

Protocol Title:

SURGX antimicrobial gel versus povidone-iodine skin incision prep for the prevention of bacterial seeding in total shoulder arthroplasty

Primary objective: skin incision preparation solution intraoperatively after the skin incision has been made will reduce the number of positive cultures after primary shoulder arthroplasty versus no intraoperative skin incision preparation. A control group with standard preoperative skin prep will be included. All patients will receive standard of care preoperative antibiotics and preoperative skin cleansing preparation prior to draping for surgery.

Hypothesis: the use of skin incision preparation solution will be more effective at reducing positive cultures compared to the control group and the SURGX antimicrobial wound gel will result in decreased C. acnes growth from intra-operative cultures when compared to the use of povidone-iodine.

#### Please save frequently

c) Describe the study design (e.g., single/double blind, parallel, crossover, control, experimental, observational, etc.). If the study is investigator-initiated, a timeline for individual subject recruitment, follow-up, and analysis for the study is required. Also, indicate if the subjects will be randomized.

This is a prospective, sequential assignment study in which patients will be blinded to the intervention. Patients will be sequentially allocated based on enrollment ID number (alternating consecutive fashion) with every third patient in the control group (no skin incision preparation) beginning with patient #1. The treatment group #1 (betadine) will be every third patient beginning with patient #2. Treatment group #2 (SURGX anti-microbial wound gel) will be every third patient #3.

d) If subjects will be given placebo, please justify placebo use. \*?HELP?\*

 N/A

#### 3. Study Procedures

a) N Is this project a multicenter study (i.e., same project is conducted elsewhere by a different investigator) OR does this study involve conduct of research at multiple sites? Is SLU acting as a coordinating center for other sites OR is the SLU PI a direct recipient of a federal grant for this research? If yes, complete and attach the Supplemental Application for Coordinating Center Activities.

Will the SLU site be participating in all parts/procedures/arms of the study?

If No, explain what SLU will NOT participate in:

#### Please save frequently

Page numbers from a sponsor's protocol/grant may be referenced in 3b, 3c, and 3d.

b) Describe all the procedures, from screening through end-of-study, that the human subject must undergo in the research project, including study visits, drug treatments, randomization and the procedures that are part of standard of care. Specify which procedures are for research and which are standard of care. Please note: The box below is for text only. If you would like to add

e-PR	ото	COL	_
------	-----	-----	---

Protocol Title:

SURGX antimicrobial gel versus povidone-iodine skin incision prep for the prevention of bacterial seeding in total shoulder arthroplasty

\_\_\_\_\_

#### tables, charts, etc., attach those files in the Attachment section (#16).

All patients must be undergoing a primary anatomic or reverse shoulder arthroplasty. Patients will be screened for iodine allergies and excluded from participation if they have this allergy. Patients will be recruited and consented preoperatively in the office prior to surgery. There is no standard of care in regards to which topical incisional adjuvant is used, if any, in shoulder arthroplasty. Common agents that are frequently used for surgical preparation include chlorhexidine and betadine (povidone-iodine). No additional procedures will be required of the study subjects. All patients will receive standard pre-operative prophylactic antibiotics. They will all receive the same preoperative external skin preparation with Hibiclens (chlorhexadine) and ChloraPrep (2% chlorhexadine gluconate / 70% isopropyl alcohol solution) prior to draping. Intra-operative irrigation will be standardized with Irrisept (chlorhexidine gluconate 0.05% in sterile water). At the time of the surgery, after the skin incision has been made with a skin knife, the dermal layer will either be not prepped or be prepped with povidone-iodine (treatment group 1) or SURGX antimicrobial wound gel (treatment group 2). At the conclusion of the case, five total cultures will be obtained. Two will be superficial and three will be deep cultures, one of which will be an implant swab. These cultures will be held in the lab for 2 weeks to evaluate for Cutibacterium acnes. After 2 weeks, we will evaluate the data to determine if there is a difference in positive cultures between the two groups. Our goal is 20 patients in each group based on previous literature assessments of skin prep solutions prior to shoulder arthroplasty. This will likely take 2-3 months to collect the appropriate number of patients and have the complete 2 week results from the lab cultures. The conclusion of the study is when we have completed the number of patients (20) in each group and final 2 weeks lab results are final. We will also collect information from medical records, as outlined in the data collection sheet.

c) If the proposed study is a clinical trial where a drug, vaccine, device or other treatment is compared to a placebo group or comparison treatment group, what are the guidelines or endpoints by which early decisions regarding efficacy or lack of efficacy can be made? For example, it may be reasonable to stop enrollment on a study when efficacy has already been clearly demonstrated, to avoid unnecessary enrollments of additional subjects. Alternatively, it may be reasonable to stop enrollment when it is clear that efficacy will never be demonstrated, given the statistical power of the study as designed. Describe the guidelines that are in place to assist in making these determinations, if relevant to the proposed study.

It has been reported in the literature that standard preoperative antibiotics and skin preparation prior to draping for the surgery does not eliminate the presence of bacteria in the wound after total shoulder arthroplasty. It is not known if this will lead to an increased risk of infections long term or if this is an incidental finding. No studies have looked at prepping the skin incision after the incision has been made to reduce this potential bacterial burden. Theoretically, if the bacterial burden is reduced at the time of surgery, this may reduce the risk of late term infection if it were to occur. The control group will receive standard pre-op skin cleansing. Since the study endpoint is presence/absence of C. acnes in the cultures, and we only plan to enroll 60 patients, we do not expect to cease enrollment early.

d) Describe how data analysis will be performed (statistical tests, methods of evaluating data) and indicate the smallest group/unit for which separate reporting will occur. For studies involving a questionnaire, if data and reliability information are available, please describe or provide references. For full board, unfunded studies describe sample size determination and power analysis. If none, please justify.

Statistics will be run through standard statistical programs, involving analyses that compare two groups of results - T-test, Chi-square etc. Our decision of sample size is based upon the literature with prior studies including comparative treatment groups of roughly 20 patients in each arm.

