## \* \* \* Background, Purpose, Study Procedures \* \* \*

#### Title

SURGX antimicrobial gel versus povidone-iodine skin incision prep for the prevention of bacterial seeding in total shoulder arthroplasty

Complete Sections 1 - 16. In sections that allow reference to sponsor protocol or grant, clearly state section and page numbers. Any information that is different or specific to the local site should be in the SLU application. Specify N/A as appropriate.

1. Background

Page numbers from a sponsor's protocol/grant may be referenced in 1a and 1b.

a) Provide an introduction and background information. Describe past experimental and/or clinical findings leading to the formulation of the study, if applicable. Investigator Initiated studies must cite references in the response provided or attach a bibliography. \*?HELP?\*

Cutibacterium acnes (C. acnes) prosthetic joint infection is a devastating and somewhat unique complication to shoulder arthroplasty. It is a very slow-growing, aerotolerant anaerobic, non-spore forming, gram-positive rod-shaped bacteria that takes up to 2-3 weeks to grow in a lab setting. There have been several studies assessing various agents in the fight to prevent C. acnes prosthetic joint infection. These agents include standard peri-operative measures typically taken when performing shoulder replacement surgery - pre-operative prophylactic antibiotics, pre-operative skin cleanse/wash, topical adjuvants (povidone-iodine, chlorhexidine, etc.), and intra-operative antibiotic powders. The overall infection rate of shoulder arthroplasty has been cited to be between 0.9-2.9%, with C. acnes being the most common bacterium in shoulder arthroplasty periprosthetic infections. Morbidity and cost associated with shoulder prosthetic joint infection is extremely high, requiring multiple surgeries and months of treatment

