The first purpose of the study is to evaluate if a dermal layer preparation will reduce positive cultures of C. acnes after primary shoulder arthroplasty. There will be a control group consisting of no skin preparation. There will be two additional comparative groups. The second purpose of this study is to compare the use of standard povidone-iodine swab versus SURGX antimicrobial gel as an application into the dermal layer after the skin incision has been made with a skin knife to see if there is a reduction in bacterial burden in the superficial and deep tissues at the end of a primary shoulder arthroplasty. Superficial and deep cultures will be held in the lab for 2 weeks to identify if bacteria is present. Our hypothesis is that the SURGX antimicrobial gel will provide a greater reduction in bacterial burden compared to povidone-iodine within the deep tissues after primary shoulder arthroplasty.

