We will be collecting 5 cultures per patient. These will included 2 superficial cultures and 3 deep cultures including one of the implant. We will hold these cultures for 2 weeks to determine the presence of Cutibacterium acnes. This bacteria is commonly present after shoulder replacement surgery (up to 73% of cases), although the clinical significance is not known. Presence of this bacteria does not mean that the patient will develop a clinical infection or indicate that antibiotics are needed. The purpose of the study is to see if this bacterial burden can be reduced for the potential reduction in the risk of late term infection if they were to occur.

е -Ркот(	PROTOCOL Biomedical Research Saint Louis University	Protocol # 3232 [name]
Protocol Title	SURGX antimicrobial gel versus povidone-iodine bacterial seeding in total shoulder arthroplasty	e skin incision prep for the prevention of
	There are no plans to contact the patients as the results of the impact on their care. However, wound cultures obtained for th in the patients' medical records.	ese cultures would not have an e study will show up as lab results
h)	Is this study subject to the NIH Genomic Data Sharing Policy? The NIH GDS policy applies to all NIH-funded research that genuman genomic data as well as the use of these data for subscription studies: genome-wide association studies (GWAS), single nupplymorphisms (SNP) arrays, and genome sequence, transcription metagenomics, epigenomic and gene expression data, irresperimechanism. Click here for more specific examples.	N enerates large-scale equent research and cleotide ptomic, ctive of NIH funding
You have not s information, ple	* * * Radioisotopes or Radiation Machines * * elected the Radioisotopes option in the General Checklist. If you base select the option to enable this section.	* I would like to add Radioisotopes
4. Radioisotop	es or Radiation Machines	
In this section,	investigators must enter all radiation usage associated with the p	protocol.

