	Identify inclusion c Age 18-90 years o Undergoing electiv	riteria. of age ve primary anatomic or reverse shoulder arthroplasty	
	Identify exclusion a	criteria.	
	revision shoulder r	replacement surgery lleray to jodine, benzalkonium chloride, or polyethylene alycc	51
i)	Compensation. Explai	in the amount and schedule of compensation, if any, that will provisions for prorating payment.	be paid for participation

e-Pro	DTOCOL	PROTOCOL Biomedical Research Saint Louis University	Protocol # 3232 [name]
Protocol 1	Fitle:	SURGX antimicrobial gel versus povidone-iodine skir bacterial seeding in total shoulder arthroplasty	n incision prep for the prevention of
n/a			
j) Desc Next cost	ribe who will cove Science will cove for the tissue wou	e r study related costs. Explain any costs that will be char e er the cost of the SURGX antimicrobial wound gel, betad und cultures (300 total cultures)	ged to the subject. ine swabs, and laboratory
k) Estimate the probable duration of the entire study including data analysis and publication. This estimate should include the total time each subject is to be involved and the duration the data about the subject is be collected. If the study is Investigator-initiated, a timeline for individual subject recruitment, follow-up, total time for subject accrual, and data analysis for the study is required.			
It wil labs take mon	l likely take 3-4 m that will take 2 we approximately 1 r ths.	onths to collect the appropriate number of patients per g seks for final results. Data analysis after the final patient nonth. Total study time to submission for publication sh	roup. Each patient will have is labs have returned will ould be no longer than 6
		* * * Risks * * *	
9. Risks			
There confid	is no research th entiality). Therefo	at can be considered totally risk free (e.g., a potential ris re, when describing the risk, the lowest level of risk is "n	k of breach of o more than minimal risk".
Page numb	ers from a spons	or's protocol/grant may be referenced in 9.1, 9.2, 9.3, an	id 9.4.
1. L cc fr F	Jse of investigation of the devices with ound in the Invest procedures that su	nal devices. Please include the clinical adverse events ( an indication of frequency, severity and reversibility. Th igator(s) brochure. NOTE: Include any likely adverse eff ibjects may experience while in the study.	(AEs) associated with each is information can often be ects associated with

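### Does reading cultures as final at 2 weeks, when the background says C. acnes may need 2-3 weeks to grow, undermine the endpoint?

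*Combined protocol and SAP*

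**What the plan says.** Section 1a (Background) describes C. acnes as slow-growing and says it "takes up to 2-3 weeks to grow in a lab setting". The hold time is then given three times, always as two weeks:

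- Section 1a, in the statement of purpose: "Superficial and deep cultures will be held in the lab for 2 weeks to identify if bacteria is present".
- Section 3b (procedures): "These cultures will be held in the lab for 2 weeks to evaluate for Cutibacterium acnes".
- Section 3g (clinical discovery): "We will hold these cultures for 2 weeks to determine the presence of Cutibacterium acnes".

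Section 3b ends the study when 20 patients per group are complete and the "final 2 weeks lab results are final". Section 8k also allows two weeks for final laboratory results. Section 11b has specimens discarded under the laboratory's own protocol once results are final. Section 3c defines what the reading feeds: "the study endpoint is presence/absence of C. acnes in the cultures".

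The text gives no reason for two weeks and does not mention recording the day of first growth. Section 16 lists a bibliography and a data collection sheet. Neither is reproduced, and either could hold that detail.

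**The concern.** The endpoint is binary and depends on when the culture is read. If the organism can take three weeks to appear and the plate is discarded after two, some true positives become negatives and cannot be recovered. With 60 patients and no power calculation, the trial has little sensitivity to lose.

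A worse possibility is a preparation that slows growth without eliminating the organism. That arm would lose more positives to the cut-off than the control arm, and the delay would look like efficacy. A 21-day hold seems a cheap remedy, because the 300 cultures are already planned and only one more week of incubation is needed.

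**Working it through.** **1. The passages side by side.** The background figure is 14 to 21 days, stated as an upper limit. The hold is 14 days. The unobserved window is at most 21 - 14 = 7 days. Fourteen days is the lower end of the stated range, so the two statements do not contradict each other. No section says that growth occurs after day 14, or how much.

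**2. There is no plan figure to reproduce.** The documents derive neither the two-week hold nor the 20 per group, and they give no alpha, power or effect size. The counts do agree: 3 x 20 = 60 patients, and 60 x 5 = 300 cultures.

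**3. Inputs for an illustration.** From the documents: 20 patients per group, five cultures per patient, and the section 3g statement that the organism is "commonly present after shoulder replacement surgery (up to 73% of cases), although the clinical significance is not known". That 73% is a maximum with no stated hold time. Assumed here: 40% positive after preparation; a patient counts as positive if any of the five cultures is; the two prepared groups are pooled (40) against control (20), following the primary objective in section 2b; Fisher's exact test, two-sided 0.05. The late share q and the week-3 false-growth rate f per culture are also assumed.

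**4. Power if the day-14 reading misses a share q of positive cultures.** With P the patient-level rate, the per-culture rate is p = 1 - (1 - P)^(1/5), which is 0.230 for 73% and 0.097 for 40%. If lateness is independent across a patient's cultures, the observed rate is 1 - (1 - p(1 - q))^5. If all of a patient's cultures are late together, it is P(1 - q).

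| q | Observed rates (independent) | Power, independent | Power, fully clustered |
|---|---|---|---|
| 0 | 73.0% v 40.0% | 60.4% | 60.4% |
| 2% | 72.2% v 39.4% | 59.6% | 58.0% |
| 5% | 70.9% v 38.4% | 58.5% | 54.8% |
| 10% | 68.7% v 36.7% | 56.8% | 50.2% |
| 20% | 63.9% v 33.3% | 54.3% | 43.7% |

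**5. Power if cultures are read at day 21 with false growth in week 3.** The observed rate is 1 - (1 - P)(1 - f)^5. At f = 1% the rates are 74.3% v 42.9% and power is 56.5%. At f = 2% they are 75.6% v 45.8% and power is 52.9%.

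**6. Break-even.** Day 21 beats day 14 only if f is below 0.5%, 0.9% or 1.6% for q = 5%, 10% or 20% under independence. Under full clustering the limits are 1.5%, 2.8% and 4.8%. The documents give neither q nor f.

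**7. If 73% and 40% are already 14-day rates.** Day-14 power stays at 60.4%. With q = 10% (independent), the 21-day per-culture rate is p/(1 - q), the patient rates become 77.2% v 43.5%, and power is 64.6%. With f = 1% it falls to 61.0%, a gain of 0.6 points.

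**8. Scale against the other unknown.** Moving the assumed prepared rate from 30% to 50% takes power from 85.8% to 32.9% with no late growth at all. Adding 10% independent lateness gives 84.0% and 30.0%, a shift of 2 to 3 points.

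**9. Timeline.** Section 8k puts "Total study time to submission for publication" at no more than 6 months. At 4 months' accrual and 1 month's analysis, a 14-day hold totals 4 + 14/30.44 + 1 = 5.46 months, and a 21-day hold 4 + 21/30.44 + 1 = 5.69 months. The margin falls from about 16 days to about 9.

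**The case for a change.** The strongest case for a change is that the protocol's own background sets a limit its procedures do not reach, on a measurement that defines the endpoint, without a reason given. The larger losses are not trivial: 20% late growth, fully clustered, takes power from 60.4% to 43.7%. If there were no true difference at 73% and a preparation only delayed growth, missing 10% to 30% of that arm's positives would create a false difference of 0.73 x 0.10 = 7 points to 0.73 x 0.30 = 22 points. Day 14 could stay primary with day 21 as a sensitivity reading, so the trade-off need not be settled in advance.

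Part of this stands. The choice of 14 days is unexplained in the text available, and the late share cannot be bounded from it. The rest does not carry a change:

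- The clustered 20% case and the delay-only case have no basis in the documents. Section 1a describes the gel as destroying bacteria, not slowing them.
- Any finite reading has a cut-off. Day 21 would narrow the exposure to delayed growth, at the price of possible contaminants. Section 3g says the study cultures appear in patients' medical records, so week-3 contaminants would appear there too.
- Whether the laboratory can hold cultures for 21 days, and whether the funding covers it, is not stated.
- A record of days to growth may already exist on the data collection sheet or in the laboratory results, so its absence cannot be asserted.

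**Conclusion.** The gap is real but small: one loose background sentence gives a range, and the plan uses its lower end consistently. The hold is the same in every arm, so the expected effect of any late growth is some loss of sensitivity. For 2% to 10% independent lateness, that is about 1 to 4 points from a 60% base. A 21-day reading may recover this or lose more, depending on a contamination rate that nobody has stated.

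These figures rest on the assumed 40% prepared rate, the use of 73% as the control rate, the pooled comparison, the any-of-five rule and an equal late share in all arms. They do not cover the gel-versus-iodine comparison at 20 v 20. They show that neither reading dominates; they do not estimate the actual loss.

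Followed as written, the plan gives a fair comparison of C. acnes growth detected within 14 days. An analyst would naturally describe the result that way and report days to positivity if the laboratory records them. The missing reason for 14 days is a gap in explanation, and no change to the plan follows.

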#### Not Applicable

X Yes, study requires RBR review

e	-PROTOCOL	PROTOCOL Biomedical Research Saint Louis University	Protocol # 32325 [name]
Pro	otocol Title:	SURGX antimicrobial gel versus povidone-iodine sl bacterial seeding in total shoulder arthroplasty	kin incision prep for the prevention of
	
 
  &nbspD this project subject to Registration may be FDAAA definition of ClinicalTrials.gov. 2) behavioral "Clinical T require personnel or Registering may be definitions here. Cor registering on Clinica information on NIH C
 
	oes this project require registration on ClinicalTrials. the NIH GCP Training Requirement? (Select "Yes" required if any of the following apply: 1) The project an "Applicable Clinical Trial", which requires registrat As of January 1, 2017, a new NIH policy mandated frials" to be registered on ClinicalTrials.gov. In addition NIH "Clinical Trials" to take GCP training every thre required for Journal Publication (ICMJE). Please revi fact the CTO at [contact] with qual Trials.gov and refer to the training page of the IRB CP Training requirements.	gov, and/or is Y if either apply) meets the tion on biomedical and on, NIH policies e years. 3) iew relevant estions about website for
8. S (inclu a)	Subject Population - In the ude description of each gr Expected age range of s 18 - 90 years of age	* * * Subject Population * * * space below, please detail the participants that you a oup requested) subjects. (For example $\geq$ 18 yrs to 90 yrs).	are requesting to recruit
b)	Number of evaluable sub sites under the direction	jects to be accrued at SLU or SLU site (this includes of the SLU PI).	s all 60
	Exceeding the number lis participants are to be acc described in 3d.	ted here is a protocol violation. Prior IRB approval is rued. If applicable, this number should be consistent	s required if additional t with your power analysis
c)	Number of evaluable sub	ijects to be accrued study wide. *?HELP?*	60

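### Section 3d pre-specifies no adjusted analysis, although arthroplasty type is known for every patient; a test stratified by type would cost almost nothing and might help

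*Combined protocol and SAP*

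**What the plan says.** Section 3d gives the whole statistical method in one sentence: "Statistics will be run through standard statistical programs, involving analyses that compare two groups of results - T-test, Chi-square etc". No regression model, stratified test, covariate or baseline-balance check appears there or elsewhere.

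Section 3c makes the outcome binary: "Since the study endpoint is presence/absence of C. acnes in the cultures, and we only plan to enroll 60 patients". Section 3b sets the size: "Our goal is 20 patients in each group based on previous literature assessments of skin prep solutions prior to shoulder arthroplasty". Section 2c sets the allocation: "Patients will be sequentially allocated based on enrollment ID number (alternating consecutive fashion) with every third patient in the control group", with the two preparations taking the next two places in turn.

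Two patient characteristics must be known for a patient to enter. Section 3b states "All patients must be undergoing a primary anatomic or reverse shoulder arthroplasty", and section 8a gives the age range as "18 - 90 years of age". Section 3b adds: "We will also collect information from medical records, as outlined in the data collection sheet". That sheet is listed among the attachments in section 16 but is not reproduced, so its variables cannot be seen.

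**The concern.** The trial pools two different operations in arms of 20. If positivity differs between anatomic and reverse replacements, an uneven mix across arms shifts the unadjusted difference in one direction, and nothing in section 3d would take that shift out. A known prognostic factor left out of the analysis also leaves avoidable variation in the comparison, in a trial with little information to spare.

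Timing matters too. If no adjusted analysis is written down and the arms turn out uneven, the investigators must either ignore the imbalance or adjust after seeing results. Section 9, item 11 (Data Safety Monitoring) schedules an aggregate review of benefit, harm and futility after the first 20 participants, so outcomes may be seen by arm well before the end.

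**Working it through.** **The plan's own figures.** 3 arms x 20 = 60, which agrees with section 8b. The choice of 20 cannot be re-derived. Section 3d rests it on precedent ("Our decision of sample size is based upon the literature with prior studies including comparative treatment groups of roughly 20 patients in each arm") and gives no significance level, power, effect or planning rate.

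**Inputs.** From the documents: 20 per arm, a binary outcome, and arthroplasty type as a two-level factor. Assumed, because the documents do not give them: the anatomic/reverse split (50/50, 80/20, 90/10), the gap in positivity between types (0, 20, 40 points), positivity of 60% v 25% in the two arms compared, and a two-sided 5% level.

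**Step 1: how often the arms differ.** For a 50/50 factor, the number of patients with one type in each arm is Binomial(20, 0.5).
- SD of the difference in proportions = sqrt(2 x 0.5 x 0.5 / 20) = 0.158, or 16 points.
- P(counts differ by 4 or more) = 0.268, or 27%.

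**Step 2: what that does to the estimate.** Shift = (difference in count / 20) x gap.
- 20-point gap: (4/20) x 20 = 4 points.
- 40-point gap: (4/20) x 40 = 8 points.

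For scale, the standard error of the unadjusted difference at 60% v 25% is sqrt(0.60 x 0.40/20 + 0.25 x 0.75/20) = sqrt(0.021375) = 0.146, or about 15 points.

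**Step 3: power of the stratified test.** In stratum k, with n1 and n0 patients per arm, N = n1 + n0, m positives in all and A positives in arm 1:
- E = n1 x m / N and V = n1 x n0 x m x (N - m) / [N² x (N - 1)].
- CMH statistic = (sum of A - sum of E)² / sum of V, without continuity correction, referred to chi-square on 1 degree of freedom.

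Simulated power, 40,000 trials per setting, 20 v 20, 60% v 25%:

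| Split | Gap | Unadjusted | Stratified | Change |
|---|---|---|---|---|
| 50/50 | 0 | 61.2% | 60.5% | -0.7 |
| 50/50 | 20 | 60.8% | 62.8% | +2.0 |
| 50/50 | 40 | 61.2% | 70.6% | +9.4 |
| 80/20 | 20 | 61.1% | 61.8% | +0.7 |
| 90/10 | 20 | 61.1% | 61.2% | +0.1 |

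With no prognostic value the loss is under 1 point at all three splits. With a 40-point gap the gain runs from about 9 points at 50/50 down to about 2 as the split becomes uneven. Type I error is about 5% or lower for both tests.

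**The case against.** The best defence is that nothing is broken. Chance imbalance is already covered by the error rate of the unadjusted test, whose null rejection rate in simulation is 4.3% to 4.5%. No document says that arthroplasty type predicts a positive culture, and none gives the anatomic/reverse split. With a 20-point gap and an uneven split the gain almost vanishes. All of this stands and limits the claim. It does not remove the reason for the change, because the cost is also close to zero and an analysis chosen in advance avoids adjusting after the event.

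A reader might infer more than the documents support:

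- *That the plan excludes adjustment.* The "etc" in section 3d leaves the list open. What can be said is that no adjusted analysis is pre-specified.
- *That imbalance could rival the product effect.* A shift of 4 to 8 points is 11% to 23% of the 35-point effect assumed here (4/35 and 8/35), and is well inside one standard error.
- *That precision is certainly being lost.* This depends on prognostic strength, which is undocumented.
- *That adjustment repairs the allocation.* Rotation by enrolment number is predictable, so patients could be enrolled selectively. Stratifying by type deals only with imbalance in type; selection on unmeasured traits remains. The binomial calculation above also assumes that type is independent of arm.
- *That more covariates would be better.* A logistic model with type and age was not simulated. For two covariates in a linear risk-difference model, an approximate calculation at 73% v 40% gives power falling from 56% to 54% if neither is prognostic, with break-even at an R² of about 0.05. Whether other useful covariates are recorded cannot be checked without the data collection sheet.

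**Conclusion.** The point holds as an inexpensive improvement. It does not show that the unadjusted test is invalid. Section 3d names only unadjusted two-group comparisons and plans no adjustment for a factor that eligibility makes known for every patient. In arms of 20, measured case-mix differences therefore stay in the estimate. A difference of 4 or more patients arises 27% of the time for a 50/50 factor and is worth 4 to 8 points for gaps of 20 to 40 points. Stratifying by type costs under 1 point of power if type is irrelevant. It gains about 0 to 2 points for a 20-point gap and about 2 to 9 points for a 40-point gap. These figures rest on assumed positivity, gap and split; the certain benefit is an adjusted analysis fixed in advance.

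**What to change.** In section 3d, state that the main patient-level analysis of each contrast is a Cochran-Mantel-Haenszel test stratified by arthroplasty type (anatomic/reverse), reported with a stratified risk difference and its 95% CI. Keep the unadjusted comparison as a supporting result. Require arthroplasty type to be recorded for every patient, adding a field to the data collection sheet if it is not already there. Settle the wording before any outcome is tabulated by arm, including for the review after the first 20 participants in section 9, item 11.

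The cost is a few sentences in the plan and a few lines of code, with no extra patients or procedures. The downside is a power loss of under 1 point if type turns out not to be prognostic. The predictable allocation needs its own remedy.
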